9 STATISTICAL METHODS

9.1 General Considerations

This study is intended to support a Phase 3 registrational trial in this patient population by providing information on the treatment effect on an unambiguous indicator of antiviral activity, i.e., the time to viral clearance, as well as to estimate the treatment effect on a number of important clinical and symptomatic disease correlates. Proof of concept will be established by a significant treatment effect on the primary endpoint of time to viral clearance. Based upon available data, a two-arm study of approximately 50 total subjects will be sufficient to provide reasonable assurance that the endpoints chosen for a confirmatory trial will elucidate treatment differences between favipiravir + SOC and SOC. Statistical significance testing will be used to assess the relative strength of evidence of the primary and secondary endpoints; given that this trial is intended as a proof of concept, a two-sided alpha-level of 0.10 will be used for significance testing.

It is important to ensure that reasonable certainty is achieved in the conclusions reached for key secondary endpoints, therefore key secondary endpoints will be adjusted for multiple statistical testing through a gatekeeping hierarchical methodology, as follows: Statistical significance for the first secondary endpoint, according to the order outlined in the endpoints section of this protocol, will be declared only if the primary endpoint has previously reached statistical significance. Subsequent endpoint analyses in the order presented will be declared significant

only if the previous endpoint in order has reached statistical significance. All analyses of secondary endpoints will also be conducted at the two-sided alpha-level of 0.10. The order of secondary endpoint analysis will be the following: the study-specific 6-point ordinal scale; time to clinical recovery; reduction in disease symptoms; reduction in oxygen/ventilation requirements.

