### 3.10. Missing, Unused, and Spurious Data

#### 3.10.1. Efficacy Data

Should missing data occur for time-to-event endpoints, such subjects will be included in the log-rank analysis as censored observations as specified in Section 4.3.1.

Missing clinical outcome data for secondary efficacy endpoints (other than time-to-event) will be handled by a multiple imputation model that contains the following variables: baseline and post-baseline parameter values, and disease severity, stratified by treatment group. Imputation of missing data will be conducted under a working assumption of missing at random (MAR), meaning that the propensity for a data point to be missing is not related to the missing data, but it is related to some of the observed data.

The imputations will be performed for post-baseline visits. The Fully Conditional Specification (FCS) method will be used, given its natural handling of both ordinal and nominal variables (Liu & De 2015). Predicted Mean Matching (PMM) (using a linear prediction model to obtain predicted values and  $k=5$  for randomly drawing from  $k^{\text{th}}$  nearest observed values to the predicted value) will be implemented under FCS (Schenker & Taylor 1996). One hundred (100) datasets will be imputed in order to estimate the treatment effect, where the median value across the imputed datasets will be used for subjects with missing endpoints.

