#### 4.3.2. Analysis of Secondary Efficacy Endpoints

##### 4.3.2.1. Analysis of Clinical Status via the Study-Specific 6-point Ordinal Scale

The first secondary endpoint of clinical status as measured by the study-specific 6-point ordinal scale at Day 15 will be analyzed by fitting a cumulative odds model, using the most appropriate approach. Clinical status will be modelled as the dependent variable (ordered from 1 to 6, as defined in [Section 1.2.6.1](#)), and treatment group and disease severity as independent variables; other factors may be added for exploratory purposes. Subjects with missing Day 15 data will have their clinical status imputed in the following manner:

- 1) If patients were discharged prior to Day 15, then their clinical status will be imputed to 'Not Hospitalized' at Day 15
- 2) If patients died prior to Day 15, then their clinical status will be imputed to 'Death' at Day 15
- 3) If there is no evidence of hospital discharge or death, clinical status at Day 15 will be imputed using the multiple imputation method described in [Section 3.10.1](#)

The odds ratios and their 90% CI will be provided. As described in [Section 3.2](#), a test at the two-sided alpha level of 0.10 will be performed for descriptive purposes.

Longitudinal analysis of the 6-point scale over time at each visit will be performed in a similar manner. Clinical status will be modelled as the dependent variable and treatment group, disease severity, visit, and the visit/treatment group interaction term as independent variables. The overall treatment odds ratio and their 90% CI will be provided, along with by-visit odds ratios and 90% CI.

Analyses using the study-specific 6-point scale will be done using the ITT population.

The analysis will also be repeated by the dexamethasone usage subgroup, where patients will be categorized as having received dexamethasone if they received it at any time prior the Day 15 analysis visit assessment.

Stacked bar charts over time will be generated to graphically display the proportion of patients in each level of the 6-point scale by treatment group for the ITT population.

By-subject data listings will be provided.

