#### 4.3.2.1.1. Sensitivity Analysis

The following sensitivity analyses are planned for supportive inference using the ITT population:

- 1) The status of clinical recovery at Day 15 analysis will be repeated using the single imputation method of Last Observation Carried Forward (LOCF) rather than the multiple imputation approach described in [Section 3.10.1](#)
- 2) Clinical status will be dichotomized over time, where subjects will be classified as either improved (Yes) or declined/no change (No) based on the 6-point scale result from the baseline visit. Subjects who are discharged or deceased over time will not contribute to subsequent timepoints. The treatment effect will be analyzed via generalized linear mixed models using SAS PROC GLIMMIX, with improvement in clinical status (yes/no) as the dependent variable, and treatment group, disease severity, and visit as independent variables. Least-squares means of the treatment group effect on the logit scale (difference on the log odds) will be utilized for analysis, where the odds ratio and corresponding 90% CI will be provided

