#### 4.3.2.5. Reduction in Oxygen/Ventilation Requirements

The frequency of requirement for any supplemental oxygen or ventilation (non-invasive, mechanical, or ECMO), as assessed daily up to 29 days and on Day 45 and 60, if possible, will be analyzed in a similar fashion as respiratory progression in [Section 4.3.2.3.1](#).

In addition, the frequency of requirement for any ventilation requirement (non-invasive, mechanical or ECMO) and either mechanical ventilation or ECMO will be analyzed in the same manner as above.

The analyses on oxygen/ventilation requirements will be performed using the ITT population.

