#### 4.3.2.6. Duration of Supplemental Oxygen, Non-Invasive Ventilation, Mechanical Ventilation, ECMO, Hospitalization, and Time in ICU

The total duration (in days) of any respiratory assistance (supplemental oxygen, non-invasive ventilation, mechanical ventilation, ECMO), hospitalization, and ICU will be analyzed using an ANCOVA model, investigating the difference in means between the treatment groups. The difference in mean durations between treatment groups will be provided, along with 90% CI. All durations are counted from randomization. In addition, the total time on any ventilation assistance (non-invasive/mechanical ventilation, ECMO), and either mechanical ventilation or ECMO will be analyzed using an ANCOVA model as above.

The exact duration will be counted. But, it was initiated prior to study enrollment, duration will be calculated from treatment start date for patients on favipiravir and randomization date for patients on SOC. The maximum value of these durations will not exceed 60 days

The analyses above will be performed using the ITT population.

Box plots for the total duration of any respiratory assistance and hospitalization will be provided by treatment group. By-subject data listings for each parameter will also be provided.

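### SAP 3.10.1 replaces each missing value with the median of its 100 imputations, which is single imputation and makes the 90% intervals too narrow wherever values are imputed

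*SAP*

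**What the plan says.** SAP Section 3.10.1 sets the scope: "Missing clinical outcome data for secondary efficacy endpoints (other than time-to-event) will be handled by a multiple imputation model". The method is fully conditional specification with predictive mean matching (k = 5), by treatment group, under missing at random. It continues: "One hundred (100) datasets will be imputed in order to estimate the treatment effect", and then "where the median value across the imputed datasets will be used for subjects with missing endpoints". Neither document mentions fitting a model in each dataset, between-imputation variance, or a pooling rule.

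The main user of this method is the Day 15 analysis of the 6-point scale (SAP Section 4.3.2.1). Subjects discharged or dead before Day 15 are first assigned a category by rule. After that: "If there is no evidence of hospital discharge or death, clinical status at Day 15 will be imputed using the multiple imputation method". The result is an odds ratio with a 90% CI. SAP Section 4.3.2.1.1 adds a sensitivity analysis that is to be "repeated using the single imputation method of Last Observation Carried Forward (LOCF) rather than the multiple imputation approach".

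The other modelled endpoints within the scope of 3.10.1 are the longitudinal 6-point scale (4.3.2.1), respiratory progression (4.3.2.3.1), oxygen or ventilation requirement (4.3.2.5; "as assessed daily up to 29 days and on Day 45 and 60, if possible") and durations (4.3.2.6; "ANCOVA model, investigating the difference in means between the treatment groups").

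**The concern.** The median clause attaches to subjects. Each missing value is therefore replaced by a single number, one completed dataset is produced, and the model is fitted once. This is an inference from the wording, but the alternative, a median of 100 treatment estimates, does not fit the sentence and would leave the CI undefined.

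Filling with a central value does two things. It discards the between-imputation variance, and it shrinks the residual spread because the filled values sit in the middle of their distribution. Standard errors come out too small.

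Two further problems follow:

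- SAP 4.3.2.1.1 presents LOCF as the single-imputation contrast to a multiple-imputation main analysis. As written, both are single imputation, and neither Day 15 result carries any uncertainty from the imputation.
- A median of 100 integer draws can fall between two ordinal categories, or equal 0.5 for a yes/no outcome. The SAP has no rule for either case.

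Protocol Section 9.1 gives one purpose of the study as "to estimate the treatment effect on a number of important clinical and symptomatic disease correlates", in support of Phase 3. Because the secondary p-values are descriptive (SAP Section 3.2), the estimates and their 90% CIs are the main secondary output. Overstated precision would pass directly into Phase 3 planning.

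**Working it through.** **Inputs from the documents.** 100 imputations, predictive mean matching with k = 5 by arm, missing at random (SAP 3.10.1); 25 per arm (SAP 3.1); two-sided 0.10 and 90% CIs (SAP 3.2, 4.3.2.1, 4.3.2.6); discharge and death assigned before imputation at Day 15 (SAP 4.3.2.1).

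**Assumed, because the documents do not give them.** The number of values imputed and the outcome distributions. The plan states no missing fraction or CI width, so it has no figure of its own to reproduce on this point.

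**Step 1: closed form for a mean difference.** Let a fraction f be missing in each arm, with uninformative predictors. The estimate then rests on n(1 − f) subjects per arm, so the true SE is σ√(2/[n(1 − f)]). The filled dataset shows a variance of about (1 − f)σ² on n subjects, so the reported SE is about σ√(2(1 − f)/n). The ratio of reported to true SE is 1 − f, and the rejection rate under no effect is 2[1 − Φ(1.645(1 − f))]:

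| f | 2% | 4% | 6% | 10% | 20% |
|---|---|---|---|---|---|
| Type I error (nominal 0.10) | 0.107 | 0.114 | 0.122 | 0.139 | 0.188 |

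Informative predictors soften this. At f = 10%, coverage of the 90% CI is 86% with uninformative predictors and 88% if they explain half the variance; at 20% it is 81% and 86%.

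**Step 2: Day 15 6-point scale, with the discharge/death rule applied first.** About 4,000 simulated trials per cell, no true effect, Monte Carlo error 0.5 to 0.6 percentage points. The imputation uses baseline score, Day 11 status and severity; the cumulative-odds model has treatment and severity. Assumed: 70% discharged and 7% dead by Day 15, or 50% and 8%; severity mix 15/65/20%. Medians falling between categories are set to the lower one.

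| Imputed, of 50 | 70% discharged: median / Rubin / complete data | 50% discharged: median / Rubin / complete data |
|---|---|---|
| 1 | 0.108 / 0.091 / 0.102 | 0.112 / 0.099 / 0.104 |
| 2 | 0.122 / 0.092 / 0.100 | 0.123 / 0.101 / 0.103 |
| 3 | 0.133 / 0.092 / 0.099 | 0.139 / 0.106 / 0.107 |
| 5 | 0.151 / 0.093 / 0.099 | 0.165 / 0.102 / 0.104 |

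At 5 of 50 with 50% discharged, the median rule reports a mean SE of 0.573 against an actual SD of 0.696 (0.573/0.696 = 0.82). Rubin's rules report 0.597 against 0.640 (0.93). The median rule also makes the estimate itself more variable. Between 1% and 4% of the medians fell between categories.

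**Step 3: duration ANCOVA.** Skewed durations, with baseline SpO2 and severity as covariates:

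| Imputed, of 50 | Median rule | Rubin |
|---|---|---|
| 2 | 0.115 | 0.105 |
| 3 | 0.124 | 0.106 |
| 5 | 0.145 | 0.114 |
| 10 | 0.167 | 0.108 |

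**Step 4: separate check by coverage of the nominal 90% CI.** 949 to 1,500 usable replicates per cell, 25 per arm; 100 imputations for the continuous model and 40 for the others. There is no discharge/death step here, and the binary model is a plain logistic regression, so this confirms direction and does not size the Day 15 effect.

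| Missing | Continuous: median / Rubin | Ordinal: median / Rubin | Binary: median / Rubin |
|---|---|---|---|
| about 6% | 0.89 / 0.91 | 0.85 / 0.90 | 0.86 / 0.91 |
| about 11% | 0.86 / 0.89 | 0.84 / 0.89 | 0.82 / 0.89 |
| about 21% | 0.83 / 0.89 | 0.75 / 0.89 | 0.74 / 0.90 |

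The median-rule interval was the narrower one in at least 98.9% of replicates in every cell.

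**Step 5: a further, smaller simulation.** Type I error for the duration ANCOVA, median against Rubin, was 0.131 v 0.100 at 5 of 50 and 0.148 v 0.107 at 10 of 50. For the Day 15 scale it was 0.122 v 0.108 at 2 of 50. The 5-of-50 ordinal cell (0.180 v 0.139) was noisy, with complete data at 0.141, and carries little weight beyond its direction.

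**The case against.** The strongest reply is that very little may be imputed at Day 15. Clinical status is recorded daily in hospital (Protocol Sections 7.1 and 13), the Day 15 analysis window runs from Day 13 to Day 17 (SAP Table 3-1), and discharged or deceased subjects are filled by rule. Protocol Section 9.6 expects little missing data in hospital and places the difficulty with discharged subjects. With 70% discharged and 7% dead, 50 × 0.23 = 11.5 subjects remain in hospital, so 5 imputed means 5/11.5 = 43% of them; with 50% and 8% it is 5/21 = 24%. This stands: the lower rows of the Day 15 table are upper scenarios. With 1 imputed, the excess over complete data is close to Monte Carlo error.

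Second, 3.10.1 describes imputation at post-baseline visits, whereas a duration is one total per subject. The stated scope covers durations on its face, but the SAP does not say how the method would work for them, so the duration figures depend on an assumed set-up. The longitudinal scale, respiratory progression and oxygen/ventilation models were not simulated in their planned form; for these only the direction is shown.

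Third, it is unclear whether 3.10.1 reaches viral load, since it refers to clinical outcome data, and an MMRM on observed data would not be affected. No claim is made for viral load or for all-cause mortality.

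Fourth, secondary p-values are descriptive and proof of concept rests on the primary endpoint. That limits the consequence, but it does not make the intervals right.

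**Conclusion.** The concern holds. As written, SAP 3.10.1 is single imputation under a multiple-imputation label, and it understates uncertainty wherever a value is imputed. The effect is zero if nothing is imputed, small at 1 or 2 of 50 (Day 15 type I error 0.11 to 0.12 against nominal 0.10) and material from about 5 of 50 (0.15 to 0.17 at Day 15; about 0.13 to 0.15 for durations). These sizes rest on assumed outcome distributions and on numbers imputed that the documents do not give. The primary log-rank test and all time-to-event endpoints handle missing data by censoring and are unaffected, as are purely descriptive summaries. The trial's formal conclusion does not change. This should be fixed because the affected intervals are meant to inform Phase 3 and the correction is cheap.

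**What to change.** In SAP 3.10.1, delete the clause that assigns the median to subjects with missing endpoints and put in its place:

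> The planned model will be fitted in each of the 100 completed datasets. Estimates (log odds ratios or mean differences) and their variances will be combined by Rubin's rules with small-sample degrees of freedom (PROC MIANALYZE with EDF) to give the estimate, 90% CI and descriptive p-value. The discharge and death assignments in Section 4.3.2.1 are made before imputation. The number of values imputed per arm and visit will be reported.

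The SAP should also name the EDF value for each model. For the ANCOVA this is the complete-data residual degrees of freedom; for the cumulative-odds and mixed models it needs an explicit choice. One added line should say how the method applies to durations. Pooling makes a rule for half-categories unnecessary, since every imputed value is then an observed category. LOCF becomes a genuine single-imputation contrast.

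The cost is a short SAP edit and one extra SAS step on datasets already planned. Intervals widen slightly: at 5 of 50 imputed, the mean SE rises by about 3 to 4% for Day 15 and 8% for durations.

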#### 3.10.2. Adverse Event Data

When tabulating AE data, partial start dates will be handled as follows:

- If the year, month, and day are all missing, then set the onset day to the date of the first dose.
- If the month and day are missing, and the year is:
  - the same as the year of first dose, then set the onset day as the first day of the month of the first dose;
  - earlier than the year of first dose, then set the onset day as December 31;
  - after the year of the first dose, then set the onset day as January 1.

- If only the day is missing, then
  - if the month/year is the same as the first dose, then set the onset day as the date of first dose;
  - if the month/year is earlier than the month/year of the first dose, then set the onset day as the last day of the month;
  - if the month/year is later than the month/year of the first dose, then set the onset day as the first day of the month.

Partial end dates will only be imputed if the year is non-missing:

- If the month and day are missing, and the year is the same as the year of the last dose then set the end day as the last day of the month of the first dose. Otherwise, set the end date as December 31.
- If only the day is missing, then set the end day as the last day of the month.

If the imputed start date is later than the imputed end date then set the imputed start date to the imputed end date.

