### 3.10.3. Prior and Concomitant Medication

When tabulating prior/concomitant medication data, partial start dates will be handled as follows:

- If the year, month, and day are all missing, then set the start date to the date of first dose.
- If the month and day are missing and the year is earlier than the year of the first dose, then set the start date to December 31. Otherwise, set the start date to January 1.
- If only the day is missing, if the month/year is earlier than the month/year of the first dose then set the start date to the first day of the month. Otherwise, set the start date to the last day of the month.

Partial end dates will only be imputed if the year is non-missing:

- If the month and day are missing then set the end date to December 31.
- If only the day is missing, then set the end day as the last day of the month.

If the imputed start date is later than the imputed end date then set the imputed start date to the imputed end date.

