#### 4.5.2. Adverse Events

All AEs will be coded using the MedDRA v23.0 coding system and displayed in tables and data listings using system organ class and preferred term. Missing and partial dates will be handled as described in [Section 3.10.2](#).

Treatment-emergent AEs (TEAEs) will be defined as those occurring coincident with start of treatment through Day 60.

In the favipiravir + SOC arm: Adverse event solicitation and recording will begin immediately following the first dose of favipiravir and will include only on-treatment (treatment-emergent) events. Any changes to a subject's health that occur between the signing of the informed consent and dosing will be recorded as updates to the subject's medical history.

In the SOC alone arm: Adverse event solicitation and recording will begin following the completion of all baseline assessments.

Clinical events related to the progression of COVID-19 will **not** be considered AEs.

Adverse events are summarized by subject incidence rates; therefore, in any tabulation, a subject contributes only once to the count for a given AE in both SOC and preferred term.

The number and percentage of patients with any TEAE, with any TEAE assessed by the Investigator as related to treatment, with any serious TEAE, and with any treatment-emergent serious AE (SAE) potentially related to treatment will be summarized by treatment group and overall.

All AEs occurring on-study will be listed in subject data listings.

By-subject listings also will be provided for the following: subject deaths, SAEs, and AEs leading to treatment/study discontinuation.

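### The SAP dates an adverse event known only by year to before first dose, and its end-date rule mixes up first and last dose; few records are likely to be affected

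*SAP*

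**What the plan says.** SAP 3.10.2 sets the dates used when adverse events are tabulated. Its onset branches are:

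- Nothing known: "If the year, month, and day are all missing, then set the onset day to the date of the first dose".
- Year only, same year as first dose: "then set the onset day as the first day of the month of the first dose".
- Year only, a later year: "after the year of the first dose, then set the onset day as January 1".
- Day missing: "if the month/year is the same as the first dose, then set the onset day as the date of first dose"; a later month goes to the 1st of that month.

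For an end date known only by year, the condition compares that year with the year of the last dose, but the instruction is "then set the end day as the last day of the month of the first dose". A closing rule moves an imputed start back to the imputed end whenever the start is the later of the two.

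SAP 4.5.2 says that treatment-emergent events "will be defined as those occurring coincident with start of treatment through Day 60". The same section, like Protocol 8.4.1, starts recording after the first dose in the favipiravir arm and after the baseline assessments in the SOC-alone arm.

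For medications, SAP 3.10.3 deals with a day-missing start in an earlier month than first dose and then adds: "Otherwise, set the start date to the last day of the month". SAP 4.3.1 classes a subject as a dexamethasone user according to receipt before the last viral clearance assessment.

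**The concern.** The year-only onset branch is out of line with its neighbours. An event with no date information is placed on the day of first dose, while one known to have begun in the right year is placed earlier. By the plan's own collection rule, an event recorded in the favipiravir arm cannot have begun before dosing, so the branch creates a date that the design rules out.

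At stake is the count of treatment-emergent events. If the flag follows the imputed date, the error can only remove events, which is the non-conservative direction for a safety table. With about 50 subjects randomized 1:1, one subject is 1/25 = 4 percentage points of an arm.

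The end-date rule names the last dose in its condition and the first dose in its result, which looks like a drafting slip. Both sets of rules are also anchored to doses that SOC-alone subjects never receive. SAP 3.5 substitutes randomization for them only for baseline and for time-to-event origins.

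**Working it through.** The documents state no figure on this point, so there is none to reproduce. The check applies the rules literally to every possible first-dose date.

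**Inputs.** The rules are those of SAP 3.10.2 and 3.10.3. The planned last dose is Day 14, that is, first dose + 13 days (SAP 1.2.1). Assumption: first-dose dates are spread evenly over the calendar. Three ranges were tried: all of 2020, April to October 2020, and all of 2021. Let *g* be the day of the month of first dose and *L* the length of that month.

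**Onset, year only, same year.** The imputed onset is *g* − 1 days before first dose, so it is pre-dose whenever *g* > 1. One date per month escapes: 366 − 12 = 354 for 2020. The shift averages 14.8 days and is at most 30. With the neighbouring rule (first-dose date) the count is 0 of 366.

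**End, year only.** The imputed end is study day *L* − *g* + 1, which runs from 1 to 31 with a mean of 15.8, although events are collected to Day 60. It precedes the planned last dose when *L* − *g* < 13, which is 13 dates per month: 12 × 13 = 156. With the month of last dose the count is 0 of 366.

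| First-dose dates | Onset before first dose | End before planned last dose |
|---|---|---|
| All 2020 | 354/366 = 96.7% | 156/366 = 42.6% |
| April–October 2020 | 207/214 = 96.7% | 91/214 = 42.5% |
| All 2021 | 353/365 = 96.7% | 156/365 = 42.7% |

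**Year crossing.** For first doses on December 19 to 31 (13 dates), Day 14 falls in January. An end recorded only as the new year matches the year of last dose and is set to December 31 of the old year, which contradicts the recorded year.

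**Closing rule.** A year-only, same-year start is the 1st of the first-dose month, so it is never later than that month's end and the rule is not triggered. The rule acts only on a start imputed to a later month or year that is paired with a year-only end. Example: first dose December 20, last dose January 2, onset and end both known only as the new year. Onset becomes January 1 and the end December 31, so onset moves to December 31. That is the wrong year but still after first dose.

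**Medication start, day missing, first-dose month.** The imputed start is the month end. It is on or after Day *k* for *L* − *k* + 1 dates per month. For 2020:

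- Day 11: 366 − 12 × 10 = 246 (67%)
- Day 15: 366 − 12 × 14 = 198 (54%)
- Day 29: 366 − 12 × 28 = 30 (8%)

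These are shares of possible dosing dates, given a missing day. They are not shares of subjects.

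**The case against.** The strongest reply is that nothing is lost. SAP 4.5.2 does not say that the flag is programmed from the imputed date. It does say that favipiravir-arm recording takes in only on-treatment events, so a sponsor could count every recorded event as treatment-emergent. The event would then stay in the tables with an impossible onset. All on-study events are listed in any case, with separate listings for deaths and serious events. This stands as a limit: a reader might infer that events do drop out of the tables, but the documents support only that they would if the flag uses the imputed date. The definition is worded by timing and has no fallback for partial dates, so that reading is the natural one.

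The second reply is rarity. Protocol 8.4.3 requires onset and resolution dates, and the schedule of assessments has events solicited daily in hospital and at each later visit. A year-only date in a 60-day study should be uncommon. This also stands; the documents give no count of partial dates.

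Three further inferences are tempting but go too far:

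- That the end-date error distorts results. An end before the last dose is not in itself wrong, and no planned table uses event end dates or durations.
- That the closing rule takes events out of the treatment-emergent window. Where it acts, the moved start is the end of the first-dose month, which is never before first dose.
- That the medication rule corrupts the primary-endpoint subgroup. SAP 3.10.3 governs tabulation, SAP 4.5.5 plans only a listing, and nothing says that the imputed dates feed the dexamethasone subgroup. If they did, misclassification would need a missing day and a last swab no later than that month end. A last swab on Day 29 leaves 8% of dosing dates exposed.

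**Conclusion.** The year-only, same-year onset branch is wrong as written. When followed, it gives a pre-dose date for about 97% of possible first-dose dates, against both the adjacent branches and the collection rule. Wrongful exclusion from the treatment-emergent tables follows only if the flag uses the imputed date. The branch does not apply to events dated to a later year, which go to January 1 and stay on or after first dose.

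The end-date branch is internally inconsistent and can give an end before the planned last dose (about 43% of dates) or in the wrong year (late-December starts). Its effect is confined to listings.

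The percentages assume evenly spread dosing dates and are conditional on a date being incomplete. The number of affected records is unknown and probably small, so this is a minor correction. The dexamethasone point is secondary and precautionary.

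**What to change.** Amend the SAP before the safety tables are programmed:

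1. In 3.10.2, set a year-only onset in the year of first dose to the first-dose date. State that the randomization date takes this role for SOC-alone subjects.
2. In the 3.10.2 end-date rule, replace the month of first dose with the month of last dose or of last contact. Last contact suits collection to Day 60 better and also works for SOC-alone subjects.
3. In 4.5.2, state how the treatment-emergent flag is derived when an onset is incomplete. If every recorded event is to count as treatment-emergent, say so.
4. For the dexamethasone subgroups, state that the month-end imputation in 3.10.3 does not decide user status when the recorded month is compatible with use before the cut-off.

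The cost is about a sentence and a line of programming for each. No data collection, sample size or primary analysis changes.
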